8.2. Study Objectives

The study objectives are to:

- 1. Evaluate, to the extent measurable in the available routinely collected data, indicators of HCP's adherence to the risk minimization measures (RMMs) in accordance with the ritlecitinib SmPC, HCP guide, and Patient Card, specifically:
 - Performing laboratory tests of lymphocyte count, platelet count, hepatitis B/C, and tuberculosis (TB) screening prior to initiation of ritlecitinib treatment
 - Performing laboratory tests of lymphocyte count and platelet count at week 4 (± 2 weeks) from initiation of ritlecitinib treatment
 - Avoiding live attenuated vaccines shortly before and during treatment with ritlecitinib
 - No use during pregnancy
 - No use in patients aged < 12 years
 - No use during serious infections
- 2. Describe the characteristics of patients before initiation of ritlecitinib treatment, in terms of:
 - Risk factors for thromboembolic events (including deep vein thrombosis (DVT), pulmonary embolism (PE), and arterial thrombosis)
 - Risk factors for malignancy
 - Risk factors for cardiovascular disease (CVD)

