9.3. Variables

Variables will include patient demographics (age and sex), comorbidities (measured by diagnoses from specialist health care at hospital encounters or treatment proxies), medication dispensings, procedures, and laboratory tests (Denmark and France only) prior to initiating ritlecitinib and monitoring tests during follow-up after treatment initiation. The maximum

lookback period for ascertaining characteristics before ritlecitinib initiation will be 12 months (365 days), but will vary for a given RMM measure, per SmPC.

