9.3.2. Indicators of Adherence to RMMs

The RMMs are described in the Risk Management Plan (13). Briefly, the RMMs recommend performing laboratory screening tests prior to ritlecitinib initiation, including lymphocyte count, platelet count, hepatitis B/C, and TB; performing laboratory tests of lymphocyte count and platelet count 4 weeks after initiation, avoiding live attenuated vaccines shortly before and during treatment, and avoiding use in pregnancy and during serious infections. Ritlecitinib is currently only indicated for those age 12 years or older.

- Lymphocyte count
- Platelet count
- Screening for TB
- Screening for viral hepatitis B and C
- Live attenuated vaccines
 - o Measles
 - o Mumps
 - o Rubella
 - Others as available in data sources
- Pregnancy
- Serious infections

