Vaccines	Vaccine type as recorded in the Danish Health Service Registry. The registry lists vaccine pathogen e.g., MMR vaccine etc. However, it is possible to identify live vaccine based on what is used according to the Danish Health Authority. This registry records vaccines that are paid by public. Travel vaccines and vaccines paid by employer will not be recorded.	Reimbursed vaccines such as MMR, chickenpox (for patients 12 months and above), BCG, Rotavirus, varicella, Dengue, and Yellow Fever not reimbursed.	Not available	

Table 1. Preliminary Definitions of the Main Study Variables

Dragnanav	ICD 10 O about an and an fair	ICD-10 codes: O80xx-	ICD-10 O	
Pregnancy	ICD-10 O chapter codes for			
	pregnancy, NOMESCO codes	O84xx (delivery),	chapter codes	
	KMCA for Caesarean and/or	Z37xx (result of	for	
	linkage to the birth registry	delivery), O01xx-	pregnancy	
	Diagnosis codes for	O07xx (abortion and	(https://icd.w	
	pregnancy ICD-10 O chapter	other abnormal	ho.int/browse	
	(https://icd.who.int/browse10/	products of	10/2019/en#/	
	2019/en#/XV)	conception)	XV)	
	(Subject to availability check:		Linkage to	
	referral codes of prenatal	CCAM codes	birth registry	
	visits at GP from the Danish	(medical acts):	may be	
	Health Services Registry)	(delivery)	considered	
	Linkage to birth registry may	JQGD010, JQGD012,		
	be considered	JQGD004, JQGD001,		
		JQGD003, JQGD008,		
		JQGD013, JQGD005,		
		JQGD002, JQGD007,		
		JQGA002, JQGA004,		
		JQGA003, JQGA005		
		(211000,0001000		
		(termination)		
		JNJD001, JNJD002,		
		JNJP001		
		(ectopic pregnancy)		
		JJFA001, JJFC00,		
		JJJA002, JJJC002,		
		JJLJ001, JJPA001,		
		JJPC001, JQGA001		
		331 0001, 3 Q 01 1001		
		Outpatient healthcare		
		code (PRS NAT):		
		(medical termination)		
		2422, 3329, 2415,		
		2416		
Serious infection	Serious infection: ICD-10 code	I.	a hospital	
	contact with a minimum of 1 overnight stay A00-B99, D73.3, E06.0,			
	E32.1, G00-G02, G04.2, G05-G07, H00.0, H44.0, H60.0-H60.3, H66-			
	H67, H70, I30.1, I40.0, J00-J22, J32, J34.0, J36, J38.3, J39.0-J39.1,			
	J44.0, J85, J86, K04.4, K04.6, K04.7, K10.2, K11.3, K12.2, K14.0,			
	K57.0, K57.2, K57.4, K57.8, K61, K63.0, K65, K65.1, K65.2, K65.9,			
	L00-L08, L30.3, M00-M01, M46.2-M46.5, M60.0, M65.0, M71.0,			
	M71.1, M72.6, M86, N10, N11, N12, N13.6, N15.1, N15.9, N30.0			
	N30.8, N34.0, N41.2, N43.1, N45.2, N45.3, N45.4, N48.2, N61, N70,			
	N73, or N75.1, U071			
	Denmark only: Z861A (the code list will be refined in the SAP to map			

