9.7. Data Analysis

This is a descriptive study and the data will be analysed and results presented separately by country. Counts and proportions for categorical variables and mean and median with ranges for continuous variables will be calculated to address the study objectives, as below. All proportions will be reported with 95% CIs.

Data sources vary in collection of laboratory test and vaccine information (data on both laboratory tests and their results are available in Denmark; data on performed laboratory tests, but not results, are available in France; laboratory data are not available in Sweden). Data on vaccines are not available in Sweden.

Counts and proportions will be calculated for:

- 1. Patients with evidence of having performed the following laboratory tests and screenings within 3 months before index date:
 - Lymphocyte count
 - Platelet count
 - Screening for TB
 - Screening for viral hepatitis B and C
- 2. Patients with evidence of having performed the following laboratory tests at week 4 (\pm 2 weeks) after index date:
 - Lymphocyte count
 - Platelet count

- 3. Patients with evidence of having received live attenuated vaccines within 4 weeks before index date
- 4. Patients with evidence of having received live attenuated vaccines during treatment with ritlecitinib
- 5. Females in whom pregnancy, as recorded in the available data sources, overlaps with ritlecitinib use
- 6. Patients aged <12 years on the index date
- 7. Patients with a serious infection before index date
- 8. Patients with evidence of having measured risk factors and the number of measured risk factors for thromboembolic events within 12 months before index date
- 9. Patients with evidence of having measured risk factors and the number of risk factors for malignancy within 12 months before index date
- 10. Patients with evidence of having measured risk factors and the number of risk factors for CVD within 6 months before index date

The windows for ascertainment of presence of specific events may be revised to reflect the local data flow.

Detailed methodology for summary and statistical analyses of data collected in this study will be documented in a SAP, which will be dated, filed, and maintained by the sponsor. The SAP may modify the plans outlined in the protocol; any major modifications of primary endpoint definitions or their analyses would be reflected in a protocol amendment.

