- The ability to ascertain whether the recommended screenings or monitoring took place is limited when using automated health databases because many of the recommendations are at the discretion of the HCP and/or because they will not be captured in administrative claims or register data. For example, it is not possible to assess whether the physician ensured that the woman was using effective contraception or was not lactating. Additionally, it will not be possible to robustly assess whether HCPs discontinued ritlecitinib in response to a patient developing an infection because, for some infections, it will be challenging to assess severity and, depending on the length of the drug holiday, the databases might not capture a discontinuation in response to an infection (e.g., if it was shorter than the anticipated duration of the prescription). Therefore, the screening and monitoring recommendations proposed for assessment in the current study represent only those which can be objectively captured in automated health databases, such as laboratory tests for key clinical values. Furthermore, in data sources in which ritlecitinib use cannot be ascertained in hospital settings, lack of use during serious infectious cannot be assessed.
- Finally, while a subset of risk factors for thromboembolic events, malignancy, and CVD can be assessed in administrative data, it is not possible to confirm whether the prescribing HCP considered the risks and benefits before initiating ritlecitinib in patients at high risk for these outcomes. Thus, an assessment of risk factors can be used to characterize the exposed population but not confirm whether the recommended screening guidelines were considered. Data on body mass index, diet, and exercise are not captured in the participating data sources and data related to smoking and alcohol use is limited and must be inferred by proxies (e.g., tobaccoand alcohol-related conditions).

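### The serious-infection indicator counts infection before the index date, while its objective concerns use during infection

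*Protocol*

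**What the plan says.** Section 8.2 of the protocol lists "No use during serious infections" as one of the six adherence measures under Objective 1. Section 9.3.2 describes the underlying recommendation in the same sense: "avoiding use in pregnancy and during serious infections". Both concern drug use and infection at the same time.

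Section 9.7 gives one analysis for this measure, item 7: "Patients with a serious infection before index date". It states no window, no condition that the infection is active at initiation, and no count after the index date. Table 1 (Section 9.3.7) defines serious infection by a code list and a hospital contact with at least one overnight stay, without reference to the timing of ritlecitinib. Section 9.3 sets a general maximum ("lookback period for ascertaining characteristics before ritlecitinib initiation will be 12 months (365 days") and says that the period varies by measure, but it gives no value for infection.

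Section 9.9 says that discontinuation in response to an infection cannot be robustly assessed. It adds that, in data sources without hospital capture of the drug, "lack of use during serious infectious cannot be assessed".

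**The concern.** The objective asks about concurrence and the measure records history. Followed as written, item 7 puts two kinds of patient in one count: those who started ritlecitinib while a serious infection was ongoing, and those whose infection had resolved before they started. Only the first group bears on the recommendation, and the output cannot separate the two. Infections that begin after initiation, the other half of what *during* means, do not enter any count.

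This is one of six adherence measures in a study that is a commitment to the EMA. Section 7 says that the results will help to show whether the risk minimisation programme met its objectives and whether it needs amending. A proportion made up of resolved and active infections cannot inform that decision on this measure, whichever way it comes out.

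**Working it through.** **1. Timing rules in Section 9.7, side by side**

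- Item 1 (baseline laboratory tests and screening): within 3 months before index.
- Item 2 (monitoring tests): week 4, plus or minus 2 weeks.
- Item 3 (live vaccines, pre-index): "Patients with evidence of having received live attenuated vaccines within 4 weeks before index date".
- Item 4 (live vaccines, on treatment): during treatment.
- Item 5 (pregnancy): a pregnancy that "overlaps with ritlecitinib use".
- Item 6 (age under 12): on the index date.
- Item 7 (serious infection): before the index date, nothing more.
- Items 8 to 10 (risk factors): within 12, 12 and 6 months before index.

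Pregnancy is the closest parallel, since it too is a measure of no use during a condition, and it is defined by overlap. Live vaccines have both a bounded pre-index window and an on-treatment count. Serious infection has neither overlap nor an on-treatment count.

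**2. Can an overlap definition be built from what the protocol already has?**

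At initiation, yes. Table 1 requires an overnight hospital stay, and Section 9.1.2 fixes the index date. Whether the index date falls inside a stay can be checked from these two. On treatment, Section 9.3.1 defines an exposure episode that runs to the end of supply plus a 90-day grace period, so overlap of stays with that episode can also be computed, subject to the limits in Section 9.9.

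**3. Illustration of size**

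The plan gives no figure for this indicator. Everything below except N is an assumption.

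- N = 385 per database, from Table 2. Check: 0.5 × 0.5 × 1.96² / 0.05² = 384.16, rounded up to 385, so the plan's figure reproduces.
- r = 1% to 5% serious infections per patient-year (assumed), spread evenly over time, at most one per patient.
- d = 5 to 14 days' duration (assumed).
- L = lookback in days: 365 (the Section 9.3 maximum) or 28 (the length used for vaccines).

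Patients counted by item 7 = N × r × L / 365. 
Patients with an infection ongoing at index = N × r × d / 365. 
Ongoing share of those counted = d / L, which depends on neither N nor r.

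- L = 365: share 5/365 = 1.4% to 14/365 = 3.8%.
- L = 28: share 5/28 = 17.9% to 14/28 = 50.0%.

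In patients, with L = 365: item 7 counts 385 × 0.01 = 3.85 to 385 × 0.05 = 19.25. Ongoing at index: 385 × 0.01 × 5/365 = 0.05 to 385 × 0.05 × 14/365 = 0.74.

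Shortening the lookback from 365 to 28 days raises the ongoing share, but under these assumptions half or more of the counted infections (50% to 82%) would still have ended before initiation. The post-index part stays at zero for any L.

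**The case against.** The strongest reply has three parts.

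First, item 7 is not blind at initiation. A patient with an infection ongoing at index will usually have been admitted before that date and so is in the count. This stands: at initiation the item is over-inclusive, and the relevant patients are mostly inside it. What it lacks is a way to identify them.

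Second, the length of the window is SAP material. Section 9.3 gives 12 months only as a maximum that varies by measure, Section 9.7 lets windows be revised, and Section 9.3.7 leaves refined definitions to the SAP. This also stands, and an unstated window alone would be no finding. But the protocol itself fixes the direction, before rather than during, and no choice of pre-index window changes that.

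Third, Objective 1 is limited to what is measurable, and Section 9.9 discloses the difficulty of observing discontinuation and hospital use. That explains much of the missing on-treatment part. It does not say that item 7 is a proxy, it does not withdraw the objective, and its hospital-use caveat covers only some data sources. Neither limit prevents checking whether a stay was open on the index date.

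Stronger readings are tempting and not supported. A reader might infer that the plan applies a 12-month window here and that almost all flagged patients would be falsely labelled non-adherent. The documents fix no such window for infection, and item 7 is not itself labelled non-adherence. A reader might also take the Table 1 entry "Denmark only: Z861A" to show that past infection is counted by design. The documents do not say what that code means, and the list is marked for refinement in the SAP, so nothing here rests on it.

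**Conclusion.** The concern holds as a mismatch between objective and measure. Item 7 combines resolved with active infections at initiation and omits infections that start on treatment, whereas the comparable pregnancy and vaccine measures handle timing properly. A shorter lookback would lessen the first fault without curing it, and would leave the second untouched.

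The size cannot be stated from the documents. The shares of 1.4% to 3.8% (365 days) and 18% to 50% (28 days) show how strongly the result depends on the lookback. They rest on assumed durations and even spread, and are not predictions of what the study would report. The mismatch itself rests on the text alone and needs none of these assumptions. The study-size calculation is unaffected.

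**What to change.** Amend Section 9.7 item 7 and the matching Table 1 row as follows.

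- **At initiation:** count patients whose index date falls between admission and discharge of a qualifying overnight stay. If an interval after discharge is also wanted, prespecify it and report it separately, since it is not overlap.
- **Earlier infection:** report serious infection before index that had ended as a baseline characteristic under Objective 2, with its lookback stated, and not as an adherence indicator.
- **On treatment:** choose one of two routes. Either count qualifying stays that overlap the Section 9.3.1 exposure episode, labelled as an upper bound on use during infection within that episode, because a temporary interruption is not visible (Section 9.9) and the episode includes the 90-day grace period. Or state, by data source, that this part is not assessable. Counting only dispensings or administrations dated inside a stay would not be enough: Section 9.9 expects mainly outpatient dispensing, so use of a supply collected before admission would be missed.

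The cost is a few lines of text and no new data. The downside is rarity. In the illustration, fewer than one patient per 385 would have an infection ongoing at index, so more cells will fall in the 1 to 4 range that Section 9.10 masks.

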9.7.1. Sensitivity Analyses

A sensitivity analysis will restrict to the subset of patients with an AA diagnosis on or up to 5 years before the index date.

9.8. Quality Control

Investigators in the respective countries will be responsible for following the internal standard operating procedures to ensure data quality and integrity, including archiving of statistical programs, appropriate documentation of data cleaning and management.

The Department of Clinical Epidemiology, Aarhus University has implemented a series of internal standard operating procedures for data management and analysis as well as staff training. At a minimum, all study documents are reviewed by a senior epidemiologist and a statistician as well as by the entire research team by the entire research team. A senior epidemiologist will supervise the project and review the output before submission to the MAH and regulator. Clinical expertise is available for appropriate interpretation of results.

All project staff members receive comprehensive orientation training and are regularly trained.

The BPE has implemented a quality management system for all its activities and is certified ISO 9001:v2015 for its activities in pharmaco-epidemiology research. CNAM data extraction will be validated using the expected population size estimated using the SNDS. All statistical logs are kept and can be provided. In the case of interim analyses, the database for the interim analysis is locked and kept for ulterior validation if needed. Independent double programming will be performed for the main criteria and analysis, and the results compared for validation.

The Centre for Pharmacoepidemiology, Karolinska Institutet has implemented a Quality System with the purpose to specify the conditions and responsibilities for the daily operations of research projects. Epidemiologists and statisticians at the centre will execute quality controls at multiple levels of the research process as per internal guidelines. At a minimum, the SAP and the statistical programming and analyses will be reviewed and supervised by a senior statistician and all study documents (protocol, report, and publications) will be reviewed by the entire research team. A senior epidemiologist will supervise the project and review the output before submission to the Sponsor. Clinical expertise is available for appropriate interpretation of results. All project staff members receive comprehensive orientation training and are regularly trained.

9.9. Limitations of the Research Methods

The limitations of the study are included below:

- While ritlecitinib is expected to be well-captured in outpatient dispensing streams, the Swedish national health registers have minimal capture of inpatient hospital administrations and dispensings, and partial capture of outpatient hospital administrations (i.e., medications administered in outpatient clinics located in hospitals) and dispensings. Similarly, in the SNDS, hospital admissions only capture administered medications that are expensive. Thus, most medications that are dispensed or administered primarily through hospital channels will be missed. As ritlecitinib is mainly expected to be dispensed in outpatient settings, this limitation is unlikely to result in a large proportion of missed exposed patients.
- Given the use of data sources from three distinct European countries, there will be variability in capture of indicators of adherence to the RMMs across the data sources. For example, data on laboratory tests and vaccinations are not available in Sweden and may be under recorded in Denmark and France. In France, only reimbursed vaccinations are recorded, meaning some vaccines (e.g., yellow fever vaccination) will be missed. All major variabilities in data elements across data sources will be described in the SAP.
- Other limitations, which are similar across many administrative data sources, include incomplete identification of ongoing pregnancies and pregnancies ending in a

termination (as they are identifiable only by pregnancy end date); underascertainment of lifestyle factors such as smoking status and smoking history; and challenges in identifying screening for TB and hepatitis B and C in all participating countries.

- While the study includes databases from multiple regions within the EU that have adequate data quality, results from the participating countries may not necessarily be generalizable to other countries in the EU.
- The ability to ascertain whether the recommended screenings or monitoring took place is limited when using automated health databases because many of the recommendations are at the discretion of the HCP and/or because they will not be captured in administrative claims or register data. For example, it is not possible to assess whether the physician ensured that the woman was using effective contraception or was not lactating. Additionally, it will not be possible to robustly assess whether HCPs discontinued ritlecitinib in response to a patient developing an infection because, for some infections, it will be challenging to assess severity and, depending on the length of the drug holiday, the databases might not capture a discontinuation in response to an infection (e.g., if it was shorter than the anticipated duration of the prescription). Therefore, the screening and monitoring recommendations proposed for assessment in the current study represent only those which can be objectively captured in automated health databases, such as laboratory tests for key clinical values. Furthermore, in data sources in which ritlecitinib use cannot be ascertained in hospital settings, lack of use during serious infectious cannot be assessed.
- Finally, while a subset of risk factors for thromboembolic events, malignancy, and CVD can be assessed in administrative data, it is not possible to confirm whether the prescribing HCP considered the risks and benefits before initiating ritlecitinib in patients at high risk for these outcomes. Thus, an assessment of risk factors can be used to characterize the exposed population but not confirm whether the recommended screening guidelines were considered. Data on body mass index, diet, and exercise are not captured in the participating data sources and data related to smoking and alcohol use is limited and must be inferred by proxies (e.g., tobaccoand alcohol-related conditions).

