7. RATIONALE AND BACKGROUND

Alopecia areata (AA) is an autoimmune disease that has an underlying immuno-inflammatory pathogenesis and is characterized by nonscarring hair loss ranging from small patches to complete scalp, face, and/or body hair loss. AA may present as: limited patchy hair loss (patchy alopecia areata), complete loss of hair on the scalp (alopecia totalis [AT]), or complete loss of hair on the scalp and the body (alopecia universalis [AU]). The affected skin usually does not have signs of inflammation.

Both males and females of all ages and races can be affected. AA is the second most common cause of hair loss, affecting approximately 147 million individuals worldwide, with a lifetime risk of all subtypes of approximately 2% (1, 2). Incidence rates of AA range from 20 to 200 per 100,000 person-years [PY(s)], and the global lifetime prevalence worldwide is estimated at 2% (2-8). A meta-analysis including articles published up to 01 September, 2018 estimated the overall pooled incidence proportion of AA in Europe as 4.92% (95% confidence interval [CI] 2.41-8.25%), and the pooled prevalence as 0.58% (95% CI 0.49-0.66%) (9). AA is associated with inflammatory diseases including asthma, allergic rhinitis, atopic dermatitis, and autoimmune diseases such as thyroiditis and vitiligo (10). The natural history and prognosis of AA are unpredictable and can be marked by remission, progression, or persistence (11, 12).

Ritlecitinib was authorized by the European Medicines Agency (EMA), on 15 September 2023, for the treatment of severe alopecia areata in adults and adolescents 12 years of age and older (13). Ritlecitinib is flagged by the Danish authorities as a medication being subject to heightened monitoring (14).

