	ICD-10-CM codes to ICD-10 equivalents whenever feasible)			

Table 1. Preliminary Definitions of the Main Study Variables

Risk factors for thromboe	mbolic events, malignancy or C	CVD			
Age 65 years or older	per date of birth				
History of thromboembolic events including VTE or ATE	ICD-10 codes I26, I260A I269 I82.2; I82.3, I82.8, I82.9 O22.3 Denmark only: O882D, O882E	3, O87.0, O87.1	, I81, I82.0,		
Malignancy (any, primary or secondary)	ICD-10 codes chapter C	ICD-10 codes chapter C, treatment codes if relevant	ICD-10 codes chapter C		
Major surgery within 90 days of index date	NOMESCO Classification of Operations on the nervous system: KA; Operations on endocrine organs: KB; Operations on the heart and large intrathoracic vessels: KF; Operations on respiratory organs, chest, mediastinum and diaphragm: KG; Breast surgeries: KH; Operations on digestive organs and spleen: KJ; Operations on the urinary tract, male genitalia and retroperitoneal tissue: KK; Operations on female genitalia: KL; Obstetric operations: KM; Operations on the musculoskeletal system: KN	CCAM codes for major surgery	•		
Combined hormonal contraceptives	ATC codes G03A		Not available (not reimbursed)		
Hormone replacement therapy	AT	C codes G03			
Obesity	ICD-10 codes E65				
Alcohol-related conditions	ICD-10 codes K70, F10				
Tobacco-use related conditions	ICD-1	0 codes J40-J47			
Diabetes	ICD-10 codes F	E10-E14, ATC codes A10	1		

Table 1. Preliminary Definitions of the Main Study Variables

Hypertension	ICD-10 codes I10-I15, treatment proxies			
Hyperlipidaemia	ICD-10 codes E78, treatment p	proxies, laboratory data (l	Denmark only)	
Coronary artery disease	ICD-10 codes I21-I25 Nordic Medico-Statistical Committee (NOMESCO) codes for coronary artery bypass graft (CABG) or percutaneous intervention (PCI): FNF, FNG, FNA, FNB, FNC, FND, FNE	ICD-10 codes I21-I25	ICD-10 codes I21-I25 Nordic Medico- Statistical Committee (NOMESCO) codes for coronary artery bypass graft (CABG) or percutaneous intervention (PCI): FNF, FNG, FNA, FNB, FNC, FND, FNE	
Chronic kidney disease	ICD-10 codes N18, potentially dialysis procedure codes	ICD-10 codes N18	ICD-10 codes N18, potentially dialysis procedure codes	
AA diagnosis	ICD	0-10 code L63		

Source of ICD-10 codes: Denmark and Sweden, inpatient (hospital) or outpatient (specialist visits); France, inpatient hospital encounters. ICD-10 codes with trailing letters are applicable in Denmark only.

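### The smoking proxy (ICD-10 J40-J47) includes asthma and bronchiectasis and omits tobacco dependence (F17), so it has poor specificity

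*Protocol*

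**What the plan says.** In Table 1 (section 9.3.7) the row "Tobacco-use related conditions" has a single entry shared by Denmark, France and Sweden: the ICD-10 block J40-J47. It lists no other diagnosis and no treatment proxy. The alcohol row just above reads "ICD-10 codes K70, F10", an organ-disease code together with a substance-use code. The diabetes row adds drug codes, and the hypertension and hyperlipidaemia rows add treatment proxies.

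Section 9.9 gives the row its purpose: "data related to smoking and alcohol use is limited and must be inferred by proxies", with tobacco- and alcohol-related conditions as the examples. The only direction of error that 9.9 names for smoking is "underascertainment of lifestyle factors such as smoking status and smoking history".

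Tobacco-related conditions appear in the malignancy list (9.3.4) and in the CVD list (9.3.5). Items 9 and 10 of section 9.7 report the share of patients with such factors and a count per patient, for example "the number of risk factors for malignancy within 12 months before index date".

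Section 7 states that "AA is associated with inflammatory diseases including asthma, allergic rhinitis, atopic dermatitis", among other conditions.

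On status and capture: Table 1 is labelled preliminary, and 9.3.7 leaves the refined country-specific definitions to the SAP. Diagnoses come from hospital inpatient or outpatient specialist contacts in Denmark and Sweden, and from inpatient encounters only in France.

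**The concern.** In the WHO ICD-10 that the protocol adopts, J40-J47 is the whole block of chronic lower respiratory disease. J41-J44 hold chronic bronchitis, emphysema and other chronic obstructive disease, which are reasonable markers of tobacco exposure. J45-J46 are asthma, J47 is bronchiectasis, and J40 is bronchitis not specified as acute or chronic; none of these marks tobacco use. The one diagnosis that records tobacco dependence directly, F17, appears nowhere in the protocol.

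This matters more here than in an arbitrary cohort, because the protocol itself links asthma to the treated disease and the indication starts at age 12. One misflag also counts twice: it adds a factor to the malignancy count and another to the CVD count. Objective 2 exists to describe how much of this risk treated patients carry at initiation, so flagging the wrong patients weakens what that objective reports.

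**Working it through.** The plan states no figure for this variable, so there is nothing to reproduce. The check has two parts.

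**1. Who the row flags, as written**

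| Patient, code recorded in the lookback | Flagged? | Evidence of tobacco use? |
|---|---|---|
| Non-smoker, asthma (J45-J46) coded at a captured contact | Yes | No |
| Non-smoker, bronchiectasis (J47) | Yes | No |
| Chronic obstructive disease (J41-J44) | Yes | Indirect |
| Tobacco dependence (F17), no lung disease | No | Direct |
| Smoker with neither code | No | Not recorded |

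Rows 1, 2 and 4 are errors that a different code list would avoid. Row 5 is the under-ascertainment that 9.9 already admits.

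**2. Illustration of size, on assumed inputs only**

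The documents give no frequency of smoking, asthma or obstructive disease. Assume:
- s = share of smokers, 15% to 25%
- sens = share of smokers with a non-asthma J40-J47 code, 3% to 10%
- a = share of users with a captured asthma code, independent of smoking, 1% to 10%
- non-smokers have no non-asthma code in the block, which leaves false flags from J40 and J47 out of the sum

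Formulas:
- flagged with asthma codes = 1 − (1 − a)(1 − s·sens)
- flagged without asthma codes = s·sens
- true smokers among the flagged = s[1 − (1 − sens)(1 − a)] / flagged
- non-smokers flagged per 385 users = 385(1 − s)a, where 385 is the per-database number in section 9.5, used only for scale

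| s | sens | a | Flagged without asthma | Flagged with asthma | True smokers among flagged | Non-smokers flagged of 385 |
|---|---|---|---|---|---|---|
| 15% | 3% | 1% | 0.45% | 1.45% | 41.2% | 3.3 |
| 15% | 3% | 10% | 0.45% | 10.40% | 18.3% | 32.7 |
| 15% | 10% | 1% | 1.50% | 2.49% | 65.8% | 3.3 |
| 15% | 10% | 10% | 1.50% | 11.35% | 25.1% | 32.7 |
| 25% | 3% | 1% | 0.75% | 1.74% | 57.0% | 2.9 |
| 25% | 3% | 10% | 0.75% | 10.67% | 29.7% | 28.9 |
| 25% | 10% | 1% | 2.50% | 3.48% | 78.4% | 2.9 |
| 25% | 10% | 10% | 2.50% | 12.25% | 38.8% | 28.9 |

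Worked line (s = 0.25, sens = 0.10, a = 0.10): 1 − 0.90 × 0.975 = 0.1225; 0.25 × (1 − 0.90 × 0.90) / 0.1225 = 0.0475 / 0.1225 = 38.8%; 385 × 0.75 × 0.10 = 28.9.

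**Direction.** The flagged share exceeds the smoking share only if a > s(1 − sens)/(1 − s·sens). The lowest threshold in the assumed ranges is at s = 0.15, sens = 0.10: 0.135/0.985 = 13.7%. The highest is at s = 0.25, sens = 0.03: 0.2425/0.9925 = 24.4%. Both lie above the largest assumed a, so in every row of the table the flagged share stays below the smoking share.

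**The case against.** **The definition is preliminary.** Section 9.3.7 sends refined definitions of all variables to the SAP, which was not available for this review, and 9.7 lets the SAP modify the plan. That is fair, and it softens the point. It does not remove it. The row states a specific range that misclassifies if followed, and a promise of country-specific refinement does not signal that asthma will be dropped or F17 added. The Danish lymphocyte codes and the serious-infection list carry their own notice that they will be refined; this row does not.

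**The label is conditions, not smoking.** True of the table row, but 9.9 uses these conditions to infer smoking.

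**Capture is narrow.** A reader might infer that asthma patients in general are counted as tobacco-exposed. The documents do not support that. Asthma managed only in primary care is not flagged, in France only inpatient coding counts, and the code must fall in the lookback. Some flagged asthma patients will also smoke.

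**The net error may still be under-ascertainment.** A reader might infer that the study will overstate tobacco-related risk and that 9.9 gives the wrong direction. Neither is shown. On the inputs above, the flagged share (about 1.5% to 12.3%) stays below the assumed smoking share (15% to 25%). Comparing the flagged share with J41-J44 alone looks more dramatic: 2% with J45-J47 only and 2% with J41-J44 give (2 + 2)/2 = 2-fold, while 8% and 0.5% give (8 + 0.5)/0.5 = 17-fold. But those inputs are assumptions too, and the ratio compares one proxy with another, not with smoking.

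**Reach is limited.** No adherence indicator, comparison or sample-size figure depends on this variable. That stands.

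**Conclusion.** The point holds as one of specificity. As preliminarily defined, the smoking proxy admits asthma and bronchiectasis and leaves out the direct tobacco diagnosis, so it can flag the wrong patients in the malignancy and CVD proportions and counts. That conclusion rests on the protocol's own text and on the meaning of its codes in ICD-10.

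Its size cannot be derived from the documents. On the assumed ranges, 3 to 33 non-smokers per 385 users would be flagged through asthma, and true smokers would make up about 18% to 78% of those flagged. These figures show only that the issue need not be trivial.

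A net overstatement of smoking is not established, and the under-ascertainment named in 9.9 may well remain the larger error. What 9.9 lacks is any mention that this proxy also yields false positives. The effect is confined to one item in two lists under the descriptive Objective 2.

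**What to change.** - In Table 1 and the SAP, restrict the respiratory codes to J41-J44, dropping J40 and J45-J47.
- Add F17. Add Z72.0 (tobacco use) and dispensed drugs for nicotine dependence (ATC N07BA) in each source that captures them.
- If asthma is of interest, report it as a separate comorbidity outside the malignancy and CVD counts.
- Use the same definition for items 9 and 10 of section 9.7. While editing, settle the CVD lookback, which is 12 months in 9.3.5 and 6 months in item 10.
- In 9.9, add that the tobacco proxy can produce false positives as well as under-ascertainment.

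This is a code-list and wording change using diagnoses and dispensings already planned, and it is cheap before data extraction starts in September 2027. The cost is a lower reported tobacco proportion. In the illustration, removing asthma codes alone takes the flagged share from about 1.5%-12.3% to 0.45%-2.5%, before whatever F17 and the other codes add, which the documents do not allow one to estimate. Some smokers now flagged only through asthma would be lost: at s = 25%, sens = 10%, a = 10%, flagged smokers fall from 4.75% of users (0.25 × 0.19) to 2.5% (0.25 × 0.10). Under the independence assumption those were chance hits. The yield of Z72.0 and N07BA in each source is unknown and should be checked, particularly in France, where outpatient data cover reimbursed claims only.
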